3.3 Secondary endpoint analysis

Secondary endpoints will be measured at baseline, discharge, 1, 6, 12, and 24 months post-procedure. Descriptive statistics will be presented at each assessment, including change from baseline to subsequent time point for selected endpoints. Paired (i.e., subjects with available data at both baseline and respective time point) and unpaired data will be presented separately. Importance will be given to the 30 day and 6 month follow-ups.

1. Tricuspid regurgitation (TR)

TR from Core Lab will be categorized into two grading systems and summarized in tables:

a. 0 = none, 1 = mild, 2 = moderate, 3 = severe

b. (Pending availability from Core Lab) 0 = none, 1 = mild, 2 = moderate, 4 = severe, 5 = massive, 6 = torrential. This grading system has more granular detail and it's recommended by Hahn and Zamorano (2017).

2. Effective regurgitant orifice area (EROA)

Descriptive statistics for regurgitant area (cm²) from Core Lab will be summarized in tables.

3. Regurgitant volume

Descriptive statistics for regurgitant volume (mL) from Core Lab will be summarized in tables.

4. Tricuspid annular plane systolic excursion (TAPSE)

Descriptive statistics for distance of systolic excursion of the right ventricle annular plane towards the apex (cm) from Core Lab will be summarized in tables.

5. Left ventricular ejection fraction (LVEF)

Descriptive statistics for LVEF (%) from Core Lab will be summarized in tables.

6. New York Heart Association (NYHA) Class

NYHA will be categorized into classes (1 = no limitation of physical activity, 2 = slight limitation of physical activity, 3 = marked limitation, 4 = unable to carry any physical activity without discomfort) and summarized in tables.

7. Six Minute Walk Test (SMWT)

Descriptive statistics for distance (m) walked will be summarized in tables.

8. Kansas City Cardiomyopathy Questionnaire (KCCQ) Short form-12

Descriptive statistics for clinical summary scores will be summarized in tables.

9. N terminal pro B type natriuretic peptide (NT-pro BNP)

Descriptive statistics for NT-pro BNP (ng/L) will be summarized in tables.

10. GOT aka aspartate aminotransferase (AST), GPT aka alanine transaminase (ALT), bilirubin

Descriptive statistics for AST (U/L), ALT (IU/L), and bilirubin ($\mu\text{mol/L}$) will be summarized in tables.

11. Blood urea nitrogen (BUN) creatinine clearance

Descriptive statistics for BUN (mg/dL) will be summarized in tables.

12. Diuretic therapy

Raw data for number of subjects currently taking each type of diuretic drug and dosage level will be presented in listings.

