3 INTRODUCTION

3.1 Tricuspid regurgitation: a "forgotten" problem

Tricuspid Regurgitation (TR) is a disorder of the heart in which the Tricuspid valve, that separates the right atrium from the right ventricle, does not close properly during systole. TR is a frequent life threatening condition associated with heart failure and poor prognosis.

TR is a poor prognostic factor. Presence of significant TR is indecently associated with about two fold increase in the risk, in heart failure patients^(1,2) Topilsky et al in a study involved 353 patients with isolated TR have showed that the outcome of isolated severe functional TR, independently of other cardiovascular or comorbid conditions, is characterized by excess mortality and excess cardiac events⁽³⁾

Significant TR is estimated to occur in more than 1.6 million people in the United States and less <1% of patients with moderate or severe TR undergo surgery annually^(3,4) despite a 1-year mortality rate of 36.1% (Figure 1) vast majority of cases are managed conservatively due to the still evolving understanding of the disease Figure 1^(5,6,7).

[figure not shown]

Figure 1. Kaplan-Meier survival curves for all patients with tricuspid regurgitation (TR). Survival is significantly worse in patients with moderate and severe TR.

It is not surprising then, that the both the ESC and AHA have changed their guidelines in recent years and urge physicians to treat TR at an earlier stage in patients with concomitant left side valve pathology requiring surgery (Figure 2)^(8,9) Recent reports also show a decrease in mortality in patients treated for isolated TR at an early stage, before they suffer NYHA IV cardiac failure^(3,11) Appropriate patient selection and proper timing for repair or replacement are crucial for optimal outcome, but objective criteria for clinical decision-making remain poorly defined.

	ESC/EACTS	AHA/ACC
Primary TR		
Symptomatic isolated severe TR without severe RV dysfunction	I	IIa
Severe TR undergoing left- side surgery	I	I
Moderate TR undergoing left- side surgery	IIa	Not mentioned
Asymptomatic isolated mild or moderate TR and progressive RV dilatation or RV function deterioration	IIa	IIb (only in severe TR)
Secondary TR		
Severe TR undergoing left- side surgery	I	I
Mild – moderate TR with dilated annulus (≥ 40 mm or >21 mm/m ²) undergoing left- side surgery	IIa	IIa (only with progressive RV dilatation or prior right heart failure)

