5.5 Statistical Considerations

5.5.1 Sample size

A sample size of up to 60 patients, enrolled in this proposed multi-center study, is considered adequate to further confirm the safety and performance of the Cardioband System in TR patients. Considerable clinical data on the safety of clinically equivalent devices exists, this will enable a comparison of the clinical data obtained in this study of the safety and performance of the Cardioband System, with literature data from prior studies.

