9 CLINICAL RISK BENEFIT EVALUATION

9.1 Expected benefits

Tricuspid regurgitation is a significant disease with one year mortality 36.1 %^(3, 4), but less <1% of patients with moderate or severe TR undergo surgery. The vast majority of cases are managed conservatively due to the excessive risk of open heart surgery^(56, 7).

Thus, there is an unmet clinical need for devices enabling to perform a valve repair in a non-invasive fashion and without cardiopulmonary bypass.

Cardioband was proved to lower the surgical risks by using established transfemoral techniques; Based on established annuloplasty surgical devices. Cardioband was showed to reduce the Mitral septo-lateral annular dimension and therefore reduce the MR. MR Reduction accompanied with improvement of the NYHA stage, 6 minute walk test and MLHFQ questionnaire.

Although there are no guaranteed benefits from participation in this study the Cardioband System is expected to allow for treatment of patients that would otherwise not undergo Tricuspid valve repair due to the invasiveness of current techniques. In addition Cardioband enable fine-tuning of the repair by adjusting the device size on a beating heart.

Given these benefits showed for mitral valve repair, there is ample justification for a prospective investigation focusing on the clinical performance and safety of the Cardioband system for treatment of the Tricuspid valve as well.

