1.5 Sample Size Justification

Reference values for calculations are based on a literature review of predicate devices and clinical experience in previous Valtech adjustable and mitral annuloplasty devices. A sample size of 60 subjects allows accurate estimates of risk associated the device (even for rare events). The sample size was selected through the width of the two-sided 95% exact confidence interval of the potential adverse event rates.

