3 STATISTICAL ANALYSIS

3.1 General considerations

There are no pre-specified hypotheses for this study.

Continuous variables will be summarized with means, standard deviations, medians, ranges, and 95% confidence intervals for the mean based on a normal distribution. Categorical variables will be summarized with counts and percentages, accompanied by 95% Clopper-Pearson (i.e., exact method) confidence intervals. In addition, graphs may be created for certain endpoints as appropriate.

Nonparametric techniques may be used if the data does not meet assumptions of parametric tests.

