3.4 Missing data handling

All statistical analysis on primary and secondary endpoints will be performed using only available data. No missing value imputation will be performed.

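### Functional results at 12 and 24 months cover only treated survivors with data, and the SAP tables do not set deaths beside them

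*SAP*

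**What the plan says.** The SAP, section 3.3, states: "Secondary endpoints will be measured at baseline, discharge, 1, 6, 12, and 24 months post-procedure". The list includes NYHA class, six-minute walk distance and KCCQ. The same section adds: "Paired (i.e., subjects with available data at both baseline and respective time point) and unpaired data will be presented separately". It gives most weight to the 30-day and 6-month visits.

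Section 3.4 limits all primary and secondary analyses to available data and says: "No missing value imputation will be performed". Section 2.3 places everything except the primary safety analysis in the as-treated cohort. Section 3.1 states: "There are no pre-specified hypotheses for this study". Neither document says how death enters a functional endpoint.

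On attrition, SAP section 4.1.2 plans a disposition table with a row for deaths before follow-up, but only for 30 days and 6 months. Later deaths would appear in the table of major serious adverse events after day 30 (SAP 4.5.3). Protocol section 5.5.3 goes further than the SAP table: it promises the numbers entering and completing each visit and the reasons for all discontinuations.

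The protocol quotes a literature mortality figure twice. Section 3.1 has "despite a 1-year mortality rate of 36.1" per cent, and section 9.1 has "Tricuspid regurgitation is a significant disease with one year mortality 36.1" per cent.

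**The concern.** The study has one arm and relies on within-patient comparison (Protocol 5.1). With no control group losing subjects in the same way, a better picture at 12 or 24 months than at baseline will be read as an effect of the device.

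The two planned presentations behave differently:

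- **Unpaired.** On the natural reading, this sets all treated subjects at baseline against those still assessed later. If subjects in worse classes die or drop out more often, the later distribution looks better even when nobody has changed.
- **Paired.** Each subject is their own reference, so a change in case mix cannot by itself produce a change. But deaths are absent, and the mean change is too favourable if those lost would have changed less favourably than those who stayed.

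At stake is the interpretation of the late functional results, not the primary safety or technical endpoints.

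**Working it through.** **Inputs from the documents.** Planned size: "A sample size of up to 60 patients, enrolled in this proposed multi-center study" (Protocol 5.5.1). Background one-year mortality: 36.1% (Protocol 3.1 and 9.1). Assessment times: SAP 3.3.

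**Inputs not in the documents, assumed here.** Mortality in this cohort, the baseline NYHA mix, class-specific mortality, and the correlation between a subject's functional change and survival.

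**The plan's own figure.** The SAP says of the 60 subjects: "The sample size was selected through the width of the two-sided 95% exact confidence interval of the potential adverse event rates". No reference rate or target width is readable, so 60 can be neither confirmed nor refuted. It serves here only as an upper limit on the denominator.

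**Step 1: deaths by 12 months** = 60 × one-year mortality.

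| Assumed one-year mortality | Deaths by 12 months | Deaths by 24 months* |
|---|---|---|
| 10% | 6.0 | 11.4 |
| 20% | 12.0 | 21.6 |
| 36.1% | 21.7 | 35.5 |

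*60 × [1 − (1 − mortality)²], which assumes a constant hazard.

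**Step 2: unpaired NYHA table with no change in any subject.** Share of a class among survivors = baseline share × (1 − class mortality) ÷ (1 − overall mortality). The assumed baseline mix for II/III/IV is 20/65/15%.

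| Assumed class mortality II/III/IV | Overall mortality | NYHA II among survivors | NYHA IV among survivors |
|---|---|---|---|
| 25/37/50% | 36.6% | 0.150/0.6345 = 23.6% | 0.075/0.6345 = 11.8% |
| 15/37/70% | 37.6% | 0.170/0.6245 = 27.2% | 0.045/0.6245 = 7.2% |
| 5/10/17% | 10.1% | 0.190/0.8995 = 21.1% | 0.1245/0.8995 = 13.8% |
| 5/15/30% | 15.3% | 0.190/0.8475 = 22.4% | 0.105/0.8475 = 12.4% |

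NYHA II therefore rises from 20% to 24–27% at the high end of mortality, and to about 21–22% at 10–15%.

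**Step 3: paired table.** In the scenario of step 2 the paired change is exactly zero. Bias needs a link between change and survival. With a true mean change of zero in all subjects, a share q dead, and correlation ρ between change and a latent survival score, the expected mean change in survivors is ρ × φ(z_q) ÷ (1 − q), in SD units, where z_q is the normal quantile at q.

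| q at 12 months | ρ = 0 | ρ = 0.3 | ρ = 0.5 |
|---|---|---|---|
| 10% | 0 | 0.06 SD | 0.10 SD |
| 20% | 0 | 0.11 SD | 0.18 SD |
| 36.1% | 0 | 0.18 SD | 0.29 SD |

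In 20,000 simulated trials of 60 at 36.1% mortality, the 95% interval for the paired change lay wholly above zero in 2.7%, 21% and 50% of trials for ρ = 0, 0.3 and 0.5. At 15% mortality the figures were 2.7%, 9.5% and 17.8%.

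**Step 4: what putting deaths in the denominator does.** If, purely for illustration, 70% of survivors are NYHA I–II, the share of all treated subjects who are alive and NYHA I–II is 0.70 × (1 − mortality): 63% at 10%, 56% at 20% and 45% at 36.1%.

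**The case against.** Several counter-arguments have force.

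- **The paired table is already a safeguard.** It shows no change in the scenario of step 2, beside an unpaired table that seems to show some. This stands. Paired bias depends on a correlation that the documents do not give.
- **The background rate is not a forecast for this trial.** A reader might infer that the protocol predicts about 22 deaths in 60. It does not: 36.1% is literature background, never a planning assumption. The exclusions include life expectancy under 12 months, severe right ventricular dysfunction, cardiac cachexia and dialysis (Protocol 6.2), which may lower mortality. Subjects who die before the primary endpoint period ends are replaced (Protocol 6.5.2). At 10–15% mortality the unpaired shift is only one to two points.
- **The artefact is small against sampling error.** Nine or ten of 38 survivors in NYHA II give exact 95% limits of about 11–40% and 13–43%. True, but the interval describes precision and does not warn of a shift in one direction.
- **Deaths are not hidden from the report.** A reader might infer that they vanish. Protocol 5.5.3 and SAP 4.5.3 show otherwise. What remains is that the SAP's disposition table stops at 6 months, short of the protocol's promise, and nothing places late deaths beside the functional results.
- **The study is descriptive.** It has no hypotheses and stresses the earlier visits. That lowers the severity, but the 12- and 24-month summaries are still planned.
- **A denominator of all attempted subjects is not available.** Subjects without an implant are followed for 6 months (Protocol synopsis) and screening failures only to discharge (Protocol 6.6). This is right, and the fix uses the as-treated cohort instead.

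**Conclusion.** The point holds as a limited reporting weakness. At 12 and 24 months the functional tables describe treated survivors with data, and the SAP's count of deaths by visit does not reach those visits. The unpaired tables can improve through selective loss alone. The paired tables cannot do so by composition, but they omit deaths and mislead if the subjects lost would have fared worse.

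On assumed inputs, the unpaired NYHA II share shifts by about 4–7 percentage points at the high end of mortality and 1–2 points at 10–15%. The paired bias at 12 months runs from zero to about 0.3 SD, depending on mortality and on a correlation that nobody has yet measured in this cohort. These figures show what could happen; they do not predict the trial's result.

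The documents do not support the stronger inference that any late improvement would be an artefact. Severity is low to moderate.

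**What to change.** Keep all planned tables and add the following to the SAP:

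1. Extend the disposition table in section 4.1.2 to 12 and 24 months, in line with Protocol 5.5.3. In the NYHA and TR tables at those visits, add rows for dead, withdrawn, and alive but missing.
2. Add a supplementary proportion, *alive and NYHA I–II*, at 12 and 24 months with an exact 95% confidence interval over the whole as-treated cohort. Count deaths as not meeting it. Give alive-but-missing subjects both ways, as lower and upper bounds. Print the baseline NYHA I–II proportion of the same cohort alongside: class II is an entry class, so an unchanged class II subject would otherwise look like a success. Show attempted-but-not-implanted subjects in a separate row, since their follow-up ends at 6 months or at discharge.
3. Label six-minute walk and KCCQ changes at these visits *survivors with data*, and show baseline values separately for subjects with and without follow-up data.

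This is a cheap improvement. It needs SAP wording and a few rows from data the study already plans to collect, with no imputation and no planned analysis displaced. The downside is longer tables and supplementary percentages that look less favourable than the survivor-only ones.

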5.3.2 Secondary endpoints

- TR grade, EROA and Regurgitant Volume (by Echocardiography)
- Tricuspid annular plane systolic excursion (TAPSE)
- Technical success
- NYHA classification
- 6-Minute Walk Distance (6MWD)
- Kansas City Cardiomyopathy Questionnaire (KCCQ)
- LVEF
- LVEDVI
- LVESVI
- NT-pro BNP
- Diuretic Therapy
- GOT, GPT (ALT), and Bilirubin
- BUN Creatinine clearance
- Activity by wearable device

Endpoints will be measured at discharge, 1, 6, 12 and 24 months post procedure and will be compared to baseline

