6.1 Inclusion criteria

Patients who participate in this study must meet all of the following inclusion criteria:

1. chronic functional tricuspid regurgitation (FTR) 2+ to 4+ on a scale of 4+ (moderate to severe) with annular diameter ≥ 40 mm with valve Systolic pulmonary pressure (sPAP) ≤ 60 mmHg
2. ≥ 18 years old
3. New York Heart Association (NYHA) Class II-IVa
4. Symptomatic despite Guideline Directed Medical Therapy (GDMT); at minimum patient on diuretic regimen
5. LVEF $\geq 30\%$
6. Patient is willing and able to comply with all specified study evaluations
7. The Local Site Heart Team concur that surgery will not be offered as a treatment option
8. Transfemoral access of the Cardioband is determined to be feasible

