2.2 Secondary endpoints*

Secondary endpoints will be measured at baseline, discharge, 1, 6, 12, and 24 months post procedure.

1. Tricuspid regurgitation
2. Effective regurgitant orifice area (EROA)
3. Regurgitant volume
4. Tricuspid annular plane systolic excursion (TAPSE)
5. New York Heart Association (NYHA) Class
6. Six Minute Walk Test (SMWT)
7. Kansas City Cardiomyopathy Questionnaire (KCCQ)
8. Left ventricular ejection fraction (LVEF)
9. N terminal pro B type natriuretic peptide (NT-pro BNP)
10. GOT aka aspartate aminotransferase (AST), GPT aka alanine transaminase (ALT), bilirubin
11. Blood urea nitrogen (BUN) creatinine clearance
12. Diuretic therapy

**Note. Although originally included in the protocol, secondary endpoints:*

- (a) Left ventricular end diastolic volume index (LVEDVI)*
- (b) Left ventricular end systolic volume index (LVESVI)*
- (c) Activity by wearable device*

will not be analyzed due to their limited relevance to main study objectives

Table 2. Summary of primary and secondary endpoints

Endpoint	Baseline	Discharge	1 Month	6 Months	12 Months	24 Months
MSAE		x	x			
Technical success		x				
Tricuspid regurgitation	x	x	x	x	x	x
EROA	x	x	x	x	x	x
Regurgitant volume	x	x	x	x	x	x
TAPSE	x	x	x	x	x	x
NYHA	x	x	x	x	x	x
SMWT	x	x	x	x	x	x
KCCQ	x	x	x	x	x	x
LVEF	x	x	x	x	x	x
NT-pro BNP	x	x	x	x	x	x
AST	x	x	x	x	x	x
ALT	x	x	x	x	x	x
Bilirubin	x	x	x	x	x	x
BUN	x	x	x	x	x	x
Diuretic therapy	x	x	x	x	x	x

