4 VARIABLE LIST FOR TABLE SHELLS

The following parameters will be summarized. Other parameters may be added as deemed necessary. [REDACTED]

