4.1.3 Demographics and Baseline Characteristics

- Age
- Gender
- Body mass index
- Society of Thoracic Surgeons (STS) score
- EuroSCORE II
- NYHA class
- NYHA class grouped
- LVEF by Core Lab
- FTR Etiology

- 4.1.4 Prior cardiovascular interventions or surgeries
 - Valve surgery
 - Percutaneous transcatheter valve replace/repair other than tricuspid
 - Coronary artery bypass graft (CABG)
 - Percutaneous coronary intervention
 - Any cardiac devices without electrodes
 - Any cardiac devices with electrodes

- 4.1.5 Non-cardiovascular risk factors
 - Diabetes
 - Dyslipidemia
 - Systemic hypertension
 - Peripheral vascular disease
 - Peripheral vascular intervention
 - Chronic lung disease (moderate to severe)
 - Chronic renal disease
 - eGFR
 - Chronic liver disease
 - Chronic anemia
 - History of endocarditis
 - Thyreosis
 - Ongoing inotropic support
 - Elevated pulmonary pressure (> 35 mmHg)
 - Pulmonary pressure
 - Frailty score
 - Prior stroke
 - Prior transient ischemic attack
 - Carotid surgery
 - Carotid intervention
 - History of smoking
 - Active malignancy
 - Any other relevant medical conditions

- 4.1.6 Cardiovascular risk factors
 - Coronary artery disease
 - Previous MI
 - Angina pectoris
 - Congestive heart failure
 - Aortic valve
 - Mitral valve
 - Pulmonic valve
 - Atrial flutter/fibrillation
 - Flutter/fibrillation ablation
 - Ventricular tachyarrhythmia

- 4.1.7 Implant procedure information
 - Cardioband implanted

- Procedure outcome
 - Any septolateral reduction
 - Total Cardioband TR time
 - Total procedure time
 - Total fluoro exposure
 - Ventilated for more than 40 hours
 - Cardioband implant size
- 4.1.8 Implant hospitalization length of stay
- Implant hospitalization length of stay
 - ICU length of stay
- 4.2 Safety endpoints
- 4.2.1 Major serious adverse events
- Any major serious adverse event
 - Death
 - Myocardial infarction
 - Cardiac tamponade
 - Device related cardiac surgery
 - Stroke
- 4.2.2 Re-hospitalization due to heart failure at 12 months
- Number of CHF-related hospitalizations in the 12 months prior to procedure
 - Total number of CHF-related hospitalizations in the 12 months prior to procedure
 - Number of HF re-hospitalizations in the 12 months post discharge
 - HF Re-hospitalization rate
- 4.3 Clinical endpoints
- 4.4.1 Technical success
- Cardioband implanted
 - Successful procedure
 - Any septolateral reduction
- 4.4.2 Vital signs
- BMI
 - Weight
- 4.4.3 Other clinical endpoints
- NYHA
 - Six Minute Walk Test

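### Diuretic therapy is a secondary endpoint to be compared with baseline, but the SAP commits only to listings and to no summary of change

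*SAP*

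**What the plan says.** Protocol 5.3.2 lists "Diuretic Therapy" among the secondary endpoints and closes the list with a general rule: "Endpoints will be measured at discharge, 1, 6, 12 and 24 months post procedure and will be compared to baseline". The synopsis repeats both.

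SAP 2.2 retains the endpoint ("12. Diuretic therapy"), and SAP Table 2 marks it at baseline, discharge and 1, 6, 12 and 24 months. The note under SAP 2.2 names three protocol secondary endpoints that will not be analysed (LVEDVI, LVESVI and wearable activity) and gives a reason. Diuretic therapy is not one of them.

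The analysis in SAP 3.3, item 12, is: "Raw data for number of subjects currently taking each type of diuretic drug and dosage level will be presented in listings". The opening paragraph of SAP 3.3 promises descriptive statistics at each assessment, "including change from baseline to subsequent time point for selected endpoints", but does not name the selected endpoints.

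Inclusion criterion 4 (Protocol 6.1) reads: "Symptomatic despite Guideline Directed Medical Therapy (GDMT); at minimum patient on diuretic regimen". Protocol 5.1 describes a single-arm study in which each patient is compared with himself or herself.

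**The concern.** The protocol asks how diuretic therapy changes from baseline. The SAP answers a different question: what each subject is taking at each visit. A listing of drug types and dosage levels, even with the number of subjects on each, is not a comparison with baseline.

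The distinction matters more here than in many studies. All subjects start on a diuretic, so a count of users can show little except stopping. The information lies in changes of dose or drug within the same subject. With no control arm, nothing else in the design shows how background diuretic treatment moved over follow-up.

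Several outcomes to be tabulated (NYHA class, walk distance, weight, edema) are ones a reader would naturally view alongside diuretic use. The planned outputs commit to no summary of that use against baseline. A summary built after the results are known would have categories chosen after the fact.

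**Working it through.** The documents state no figure for diuretic therapy, so there is none to reproduce. The check is a comparison of texts, followed by a short calculation of what the missing table would deliver.

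**1. Commitment against delivery**

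| Element | Source | Content for diuretic therapy |
|---|---|---|
| Endpoint status | Protocol 5.3.2; SAP 2.2, item 12 | Secondary endpoint in both |
| Time points | Protocol 5.3.2; SAP Table 2 | Baseline plus 5 follow-ups |
| Comparison with baseline | Protocol 5.3.2 | Stated for the secondary endpoints as a group |
| Form of output | SAP 3.3, item 12 | Listings only |
| Form of output, items 1 to 11 | SAP 3.3 | Summary tables for all 11 |
| Change from baseline | SAP 3.3, opening paragraph | Unnamed selection of endpoints |
| Table-shell variables | SAP 4.1 to 4.7, visible text | No diuretic or medication variable |
| Data collected | Protocol Table 4 | Medication profile at baseline, discharge, 30 days and 6, 12 and 24 months |

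Comparisons with baseline implied by the protocol: 5. Comparisons the SAP commits to: 0. What it offers instead is a listing of up to 60 subjects × 6 time points = 360 subject-visits.

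**2. What the output list contains**

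SAP 4.4.2 and 4.4.3 name weight, NYHA class, "Six Minute Walk Test", edema and KCCQ. Diuretic use has no counterpart there. The section does say "Other parameters may be added as deemed necessary", which permits a table without promising one.

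**3. Would a table of change be informative at this sample size?**

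SAP 3.1 specifies Clopper-Pearson 95% intervals for categorical variables. For x subjects out of n, the lower limit is the 0.025 quantile of Beta(x, n − x + 1) and the upper limit is the 0.975 quantile of Beta(x + 1, n − x). The proportions below are assumptions, because the documents give none.

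| Assumed subjects in a category (e.g. dose increased) | Exact 95% CI |
|---|---|
| 6/60 (10%) | 3.8% to 20.5% |
| 12/60 (20%) | 10.8% to 32.3% |
| 18/60 (30%) | 18.9% to 43.2% |
| 30/60 (50%) | 36.8% to 63.2% |
| 6/30 (20%, if only 30 subjects have paired data) | 7.7% to 38.6% |

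At n = 60 the intervals are about 17 to 26 percentage points wide, and about 31 points wide for 6/30. That is coarse, but adequate for a descriptive statement of whether dose increases were few or common. These rows use a whole-cohort denominator; a drug taken by fewer subjects would have wider intervals.

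**4. Does the summary need a conversion between drugs?**

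No. Direction of change within one drug is defined by that drug's own dose at baseline and at the visit. Additions and switches are events that can be counted. Only a single net change per subject across several drugs would need a conversion, and the protocol's comparison does not require one.

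**The case against.** The strongest reply is that this is a small feasibility study with no hypotheses (SAP 1.2 and 3.1), whose objectives are safety and technical success. A listing may then suffice for a lower-order endpoint. The protocol's closing sentence is also generic: its list includes technical success, which has no baseline value. And SAP 3.3 leaves room for diuretics among the selected endpoints, SAP 4 leaves room for further tables with redacted text beside that clause, and a patient reader could trace changes through the listing.

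Much of this limits the size of the point. No primary result, error rate or decision rule is affected. Weight and edema are not protocol secondary endpoints and appear only in the table shells. The redaction makes absence from the shells weak evidence on its own.

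The core stands. Diuretic therapy has a baseline value, so the protocol's sentence applies to it in its ordinary sense. Item 12 specifies listings where every other item specifies tables, and the open clauses commit to nothing. The request is itself descriptive, so the lack of hypotheses does not answer it.

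A reader might go further and infer that diuretic change is the main rival explanation for any improvement, or that outcomes should be split by whether diuretics rose or fell in order to isolate a device effect. The documents do not support this. They contain nothing from which to size such confounding. Diuretic change occurs after the procedure and may itself respond to symptoms, weight or edema, so a split would condition on a possible consequence of the outcome. A subject with one drug raised and another lowered could not be placed without a conversion. Protocol Table 4 also schedules no NYHA class or walk test at discharge, so the split could not be made there.

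**Conclusion.** The point holds as a gap between protocol and SAP in one secondary endpoint: none of five comparisons with baseline is committed to, and the SAP does not declare the omission as it does for the three endpoints it drops. The effect is on interpretation: changes in NYHA class, walk distance, weight and edema will be presented without planned context on diuretic change.

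It would be too strong to say that these outcomes cannot be interpreted at all. The medication profile is collected at the relevant visits, so a post hoc summary remains possible. What is missing is a prespecified one. Nor do the documents show that the SAP abandoned the endpoint, since it stays in SAP 2.2 and Table 2.

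The conclusion assumes that the redacted text in SAP 4 does not already define a diuretic change table, and that dose is recorded in the medication profile, as item 12 presupposes. This is a cheap improvement and not a threat to the study's primary conclusions.

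**What to change.** Keep the listing, and add to SAP 3.3, item 12, a paired descriptive table at discharge and at 1, 6, 12 and 24 months:

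- For each diuretic, give the number and percentage of subjects whose total daily dose was increased, unchanged, decreased or stopped against baseline, or for whom the drug was newly added or switched to.
- Make no conversion between drugs. Report switches and mixed changes (one drug up, another down) in separate rows.
- State the denominator for each row, limited to subjects with medication data at both baseline and the visit. Attach the exact 95% intervals of SAP 3.1.
- Place the table beside the clinical outcome tables, described as context only. Do not stratify outcomes by diuretic change or draw a causal reading from it.

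The cost is a few lines of SAP text and one table, from data that Protocol Table 4 already schedules. The drawback is that, without a common dose scale, switches and mixed changes remain unresolved as to net direction, and some rows will hold few subjects. This concerns analysis and reporting only, not how diuretics are managed.
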